15.3.5. Annual Safety Updates

Once a year the sponsor/designee will submit an annual Development Safety Update Report (DSUR) to the Regulatory Authorities and main RECs/IRBs that lists all suspected serious adverse reactions occurring throughout the time period.

15.3.6. Deaths

The cause of death of a patient in a clinical study, unless it is associated with disease progression, is considered a SAE whether the event is expected or associated with the IMP. The reporting periods for SAEs are detailed in Section 15.2.2.

15.3.7. Procedures for Handling Special Situations

15.3.7.1. Pregnancy

As detailed in the inclusion/exclusion criteria, patients of childbearing potential who are not using adequate contraception will not be invited to participate in this study. Female patients of childbearing potential must have a negative serum pregnancy test within 3 days prior to the first dose of bemcentinib. In the event of any pregnancies occurring in female patients, or in BGBC003 v10.0 (US);

the partners of male patients during the study, the pregnancy must be reported to the Syneos Health Safety and Pharmacovigilance Global Safety mailbox [contact] by the investigational staff within one working day of their knowledge of the event using a Pregnancy Notification Form.

The reporting period for pregnancies will start with the first study-related procedure and end 28 days after the final administration of bemcentinib.

Any female patients who become pregnant whilst taking part in the study will be withdrawn, whilst patients whose partners become pregnant can remain in the study. A patient who completes or withdraws from the trial before the full term of their/their partner's pregnancy will be asked to consent to their doctor providing the sponsor with follow-up information concerning the pregnancy and its outcome.

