9.3.4. Follow Up

An AE will be monitored for 28 days after the last dose of bemcentinib although only events considered to be related to treatment need to be recorded in the eCRF between the last administration of bemcentinib and the end of the 28 day follow up period. If bemcentinib-related toxicities continue beyond the follow up period, patients will be followed until all bemcentinib-related toxicities have resolved to <Grade 1, stabilized or returned to baseline. If necessary, follow up monitoring for AEs may be conducted over the telephone.

SAEs with a suspected relationship to bemcentinib will be collected beyond the 28-day follow-up period until the event is resolved to \leq Grade 1, stabilized or returned to baseline.

All patients that have permanently discontinued study treatment for whatever reason must be followed for survival. The investigator or designee must confirm with the patient at the time of the Final Study Visit how the patient will be followed for survival (e.g. contact with family or

health care provider). Survival follow-up must be conducted at least every 3 months by the investigator or designee and the date-of-death reported in the eCRF.

All subsequent anticancer therapy for AML or MDS must be reported in the eCRF.

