9.5. End of Study

Except in the case of early termination (Section 9.4), the end of the study is defined as the date when all patients have an OS event, unless the Sponsor terminates OS follow-up once all patients have discontinued study treatment. Should the last patient enrolled to the study be continuing to receive bemcentinib 52 weeks from their Cycle 1 Day 1, the Sponsor may choose to lock the data base to that point and prepare the clinical study report (CSR). Data collected as part of this study after this point, will be reported as an addendum to the CSR.

A final CSR will be prepared when the last patient has completed their Final Study Visit and the database is locked. The Statistical Analysis Plan (SAP) will be finalized and signed before database lock.

Patients will continue to be followed for suspected SAEs until these are resolved to ≤ Grade 1, stabilized or returned to baseline. Refer to Section 15.2.2 for SAE reporting after the end of study.

10. Selection of Subjects

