5. Female patients of childbearing potential must have a negative serum pregnancy test within 3 days prior to taking their first dose of bemcentinib. Male patients and female patients of reproductive potential must agree to practice highly effective methods of contraception (such as hormonal implants, combined oral contraceptives, injectable contraceptives, intrauterine device with hormone spirals, tubal ligation, total sexual abstinence, vasectomy) throughout the study and for ≥3 months after the last dose of bemcentinib. Female patients are considered NOT of childbearing potential if they have a history of surgical sterility or evidence of post-menopausal status defined as any of the following:
 - a) Natural menopause with last menses >1 year ago
 - b) Radiation induced oophorectomy with last menses >1 year ago
 - c) Chemotherapy induced menopause with last menses >1 year ago

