11.2. Screening

During screening, the following procedures will be performed:

- Obtain written informed consent
- Demographic data, including date of birth, sex, height, and race
- Medical and surgical history
- Concomitant medication
- Physical examination, including weight
- Echocardiogram or MUGA scan
- Vital sign measurements (systolic and diastolic BP, heart and respiration rate and temperature)
- Serial 12-lead ECGs, in triplicate (<5 minutes apart), performed after the patient has been supine for >10 minutes)
- ECOG performance status [Appendix 1]
- Collection of blood sample for hematology (including neutrophil and platelet count), clinical chemistry profile
- Coagulation panel
- Routine urinalysis
- Serum pregnancy test, where appropriate
- BM aspirate for confirmation of the diagnosis and baseline sample for pharmacodynamic biomarker analyses

Male patients and female patients of reproductive potential must agree to practice highly effective methods of contraception throughout the study and for ≥ 3 months after the last dose of bemcentinib. Highly effective methods of contraception are defined as:

- Hormonal implants, combined oral contraceptives, injectable contraceptives,

- An intrauterine device with hormone spirals
- Tubal ligation
- True total sexual abstinence
- Vasectomy

If it is not possible to use one of these highly effective methods of contraception two barrier methods used in conjunction are acceptable.

In order to reduce the risk of tumor lysis syndrome all patients will be asked to drink up to two liters of fluid in the 24-hour period prior to starting treatment with bemcentinib and on Day 0, Day 1, Day 2 and Day 3. All patients will receive treatment with allopurinol (or equivalent) for at least the first week of treatment or until their serum uric acid is within the normal range or has returned to baseline levels.

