13.1. Clinical Safety Assessments

Before being entered into the study, patients will be assessed to ensure that eligibility criteria are met. Patients not meeting the criteria must not be entered into the study.

The following tests and assessments will be performed at times specified in the relevant Schedule of Events (Tables 4-6) in Section 11 and at any other time required in the opinion of the investigator:

- Serum pregnancy test on women of childbearing potential (Screening only)
- Physical examination
- Vital sign measurements (systolic and diastolic BP, heart and respiration rate and temperature)
- Serial 12-lead ECGs, in triplicate (\leq 5 minutes apart), performed after the patient has been supine for \geq 10 minutes)
- AE and SAE recording
- Concomitant medication and procedures recording
- Echocardiogram or MUGA scan

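### Required pregnancy reporting stops 28 days after the last bemcentinib dose, although contraception is required for at least 3 months: about 69% of the minimum post-dose contraception window has no required reporting

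*Protocol*

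**What the plan says.** **Contraception.** Protocol Section 10.1, criterion 5, asks male patients and female patients of reproductive potential to use highly effective contraception "throughout the study and for ≥3 months after the last dose of bemcentinib". The synopsis has the same requirement, and Section 11.2 repeats it: "effective methods of contraception throughout the study and for ≥ 3 months after the last dose of bemcentinib".

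**Pregnancy reporting.** Section 15.3.7.1 covers pregnancies in female patients and in partners of male patients, with notification within one working day of site staff learning of the event. Its scope is worded as "the partners of male patients during the study, the pregnancy must be reported". The next paragraph sets the limits: "The reporting period for pregnancies will start with the first study-related procedure and end 28 days after the final administration of bemcentinib". The section also plans for outcomes: a patient who leaves the trial before the pregnancy reaches term "will be asked to consent to their doctor providing the sponsor with follow-up information concerning the pregnancy and its outcome".

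**After day 28.** The Final Study Visit is 28 days after treatment stops, and Section 11.4 lists no pregnancy test there. Under Section 13.1 and the schedules of events, testing takes place at screening, or on Day 1 if not done in the preceding 3 days. After that, "Survival follow-up must be conducted at least every 3 months by the investigator or designee", with survival status and later anticancer therapy as the stated content (Sections 9.3.4 and 11.5). Section 9.5 says that, barring early termination or a sponsor decision to stop survival follow-up, "the end of the study is defined as the date when all patients have an OS event".

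The SAP lists serum pregnancy test results but does not address pregnancy reporting.

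**The concern.** The protocol asks patients to avoid conception for at least 3 months after the last dose but requires sites to report pregnancies for only 28 days of that time. A pregnancy in a patient or a male patient's partner that begins between day 29 and month 3 falls inside the contraception period and outside the reporting period. Under the stated rule, the site need not notify it, and the planned outcome follow-up has nothing to start it.

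Two unclear points in Section 15.3.7.1 make this worse. The text does not say whether a pregnancy must be conceived or recognised within the 28 days, so one conceived in week 3 and recognised in week 6 can be handled either way. And a duty to report pregnancies during the study, read with Section 9.5, reaches into survival follow-up, while the cut-off in the same section does not.

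At stake is the safety record of a new kinase inhibitor. Patients aged 18 and over are eligible and partners are in scope. Uncomplicated pregnancies and normal births also matter, because an adverse outcome cannot be interpreted without them.

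**Working it through.** The plan gives no figure for this point, so there is nothing to reproduce. The check is a day count and a comparison of texts.

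**Inputs.**
- Reporting period after the last dose: 28 days (Section 15.3.7.1).
- Contraception window after the last dose, W: at least 3 months (Sections 10.1 and 11.2). Assumption: 3 months is 84 days (12 weeks) to 92 days.

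**Share of the post-dose window without required reporting** = (W − 28) / W.

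| W (days) | Uncovered days | Share |
|---|---|---|
| 84 | 56 | 66.7% |
| 89 | 61 | 68.5% |
| 90 | 62 | 68.9% |
| 91.3 | 63.3 | 69.3% |
| 92 | 64 | 69.6% |

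Since the requirement is at least 3 months, these are minimum shares for the post-dose window.

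**Share of the whole contraception period.** Contraception also applies throughout treatment, when reporting is required. With time on treatment T, the share is (91.3 − 28) / (T + 91.3). The documents do not give T, so these are assumed values in 21-day cycles:
- 1 cycle: 63.3 / 112.3 = 56%
- 3 cycles: 63.3 / 154.3 = 41%
- 6 cycles: 63.3 / 217.3 = 29%
- about 52 weeks (364 days): 63.3 / 455.3 = 14%

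**Does another text close the gap?**
- *Serious adverse events.* A congenital anomaly is a serious event (Section 15.1.3). Section 15.2.2 collects serious events suspected to be related to bemcentinib without an end date; Section 9.3.4 is narrower and stops at resolution, stabilisation or return to baseline. This route needs both a serious outcome and suspected causality. Section 15.2.2 is written for events experienced by a patient, so it does not clearly reach the child of a male patient's partner.
- *The words on pregnancies during the study.* These could extend the duty to survival follow-up, but the explicit 28-day limit in the same section contradicts that reading.
- *Scheduled contacts.* No pregnancy test or pregnancy question is listed after Day 1 of Cycle 1.

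A pregnancy without a serious, suspected-related outcome therefore has no clear reporting route after day 28.

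**The case against.** The 28 days is not arbitrary. It matches the collection windows for adverse and serious adverse events (Sections 15.2.1 and 15.2.2) and the Final Study Visit. Most cohorts enrol patients unsuitable for intensive chemotherapy because of advanced age or co-morbidity, so few pregnancies are expected. No endpoint, DLT rule or analysis depends on them. All of this stands, and it limits the importance of the point. It does not explain why reporting is shorter than the contraception period.

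Stronger readings are tempting, and the documents do not support them:
- *That these pregnancies are never collected.* The serious-event route and the duty covering pregnancies during the study both cut against that. What is missing is a clear requirement to report.
- *That two thirds of the whole contraception period is uncovered.* The 69% holds for the minimum post-dose part only.
- *That the protocol declares 3 months of fetal risk, so fetal exposure goes unreported.* The protocol gives no reason for the 3 months, which may include a margin. From the mean half-lives of 45.6 to 88.7 hours in Section 7.2.2, 28 days (672 hours) is 672/88.7 = 7.6 to 672/45.6 = 14.7 half-lives. For the one subject at 165 hours (Section 7.2.3) it is 672/165 = 4.1. These are single-dose data in healthy men and do not address effects on gametes, so they settle the matter in neither direction. The protocol itself does not offer a washout argument for the 28 days.
- *That a pregnancy conceived before day 28 and recognised later is lost.* The text is ambiguous, and a reading by conception fits it equally well.
- *That decitabine exposure in Part B3 adds weight.* Section 16.8 says that part is complete, so an amendment would not change it.

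**Conclusion.** The mismatch is real and unexplained. Required pregnancy reporting covers 28 days of a post-dose contraception window of at least 3 months, which leaves about 69% of the minimum window (67 to 70% for 84 to 92 days) without required reporting, apart from related serious outcomes such as a birth defect. Section 15.3.7.1 is also unclear on conception versus detection, and its cut-off conflicts with its own reference to the study period once Section 9.5 is applied.

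The size rests only on the conversion of 3 months into days. This is a gap in safety data collection with small expected numbers. Sample size, type I error and the efficacy analyses are unaffected. It is worth correcting because the rule, followed exactly, leaves pregnancies within the protocol's own contraception period without required notification or outcome follow-up, and the correction is cheap.

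**What to change.** Reconcile Section 15.3.7.1 with Sections 10.1 and 11.2, taking the contraception requirement as it stands; no view is offered on its length.

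1. Run the pregnancy reporting period to the end of the contraception period already required. As that is worded as a minimum, state one explicit end point. With the 3-month minimum, reporting lengthens by 61 to 64 days (from 28 to 89–92 days after the last dose) and the uncovered share of the minimum window falls to zero.
2. State that the period covers pregnancies conceived within it, whenever they are recognised, and align the reference to pregnancies during the study with that definition.
3. Add a pregnancy question (patient or partner) at the first survival contact at or after month 3, where the patient can be reached directly. A contact before month 3 would not cover the full window.
4. Check the other country protocols for the same text. SAP Section 1 lists four (Germany, Norway, United States, Italy), and only the US one was available here.

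The cost is an amendment line, possibly in each country protocol, one question at an existing contact, and slight extra pharmacovigilance work. Capture will stay incomplete. The synopsis allows survival status to come from relatives, community providers or public records; patients who withdraw consent or are lost are not followed; and the sponsor may end survival follow-up once all patients are off treatment.

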15.3.8. Medical Emergency

In a medical emergency requiring immediate attention, study staff will apply appropriate medical intervention according to standard medical practice. The investigator/designee should contact BerGenBio's Medical Monitor if guidance is needed to manage a case particularly if the medical emergency is suspected to be related to the IMP.

15.3.8.1. Unblinding for a Medical Emergency

Not applicable.

15.4. Investigator's Safety Responsibilities

The investigator's responsibilities include the following:

- Monitor and record all AEs, including SAEs, regardless of the severity or relationship to bemcentinib
- Determine the seriousness, relationship and severity of each event
- Determine the onset and resolution of each event
- Complete an SAE form for each SAE as outlined in Section 15.2.2
- Pursue SAE follow-up information actively and persistently
- Ensure all AE and SAE reports are supported by documentation in the patient medical records
- Report SAEs to their local REC/IRB, as required by local law

15.5. Sponsor's Safety Responsibilities

The sponsor's responsibilities include the following:

- The ongoing safety evaluation of the IMP
- Reporting of SUSARs to the Regulatory Authorities, main REC/IRB and investigators according to required timelines as outlined in Section 15.3.4
- Submission of the annual DSUR to the Regulatory Authorities and main REC/IRB

15.6. Overdose

Study drug overdose is the accidental or intentional use of the drug in an amount higher than the dose being studied. An overdose or incorrect administration of study drug is not an AE unless it results in untoward medical effects. An overdose is defined by a boundary of 15% above the prescribed dose of any medicinal product.

Any study drug overdose or incorrect administration of study drug should be noted on the Study Drug Administration eCRF. All AEs associated with an overdose or incorrect administration of study drug should be recorded on the AE eCRF. If the associated AE fulfills serious criteria, the event should be reported to the Sponsor immediately (i.e., no more than 24 hours after learning of the event).

16. Statistical Methods and Determination of Sample Size

Detailed statistical analysis information will be provided separately in the SAP. Any deviations to the planned analyses specified within the SAP, will be justified in writing and presented within the final CSR.

In the Tables, Listings and Figures presented in the CSR, patients enrolled in Part A will be reported separately. Where appropriate, the data for patients who received the MTD during Part A will be combined with that for patients who received the MTD in Part B for the purpose of data summarization. A clear distinction will be made in the relevant Tables to differentiate between the cohort who received the MTD during the dose escalation phase of Part A, the MTD cohort from the cohort expansion phase in Part A, and the combined MTD cohort.

If necessary, after the clinical phase of the study has been completed, a decision will be made between the sponsor and the study statistician regarding management of missing values, data for withdrawn patients and data for protocol violators.

Interim reports will be prepared as required during the study. The study will be completed when all patients have an OS event, unless the Sponsor terminates OS follow-up once all patients have discontinued study treatment. The database lock will take place when all data to this point, are reconciled, and the CSR will be generated. Should the last patient enrolled to the study be continuing to receive bemcentinib 52 weeks from their Cycle 1 Day 1, the Sponsor may choose to lock the data base to that point and prepare the CSR. Data collected as part of this study after this point, will be reported as an addendum to the CSR.

16.1. Description of Objectives

Please refer to Section 8.1.

16.2. Description of Endpoints

Please refer to Section 8.2.

16.3. Demography and Baseline Disease Characteristics

The Enrolled Population will include all patients who have signed the ICF and enrolled into the study. The enrolment date will be defined as the date of the first protocol-defined screening procedure. All patients in the Enrolled Population will be accounted for in patient disposition. Patient disposition will be summarized by dose group. Medical history and prior medications will be tabulated.

Data from patients who fail screening will not be collected. The exception to this will be patients who experience an SAE due to a Screening assessment. Such events should be reported and will be recorded in the CSR.

16.4. Safety

16.4.1. Analysis Population

The safety analysis set (SAS) will be defined as all patients who receive at least one dose of bemcentinib. The SAS will be analyzed by dose group or combination in Part B.

Patients enrolled to Part A who meet the eligibility criteria for Part B1 and who receive the RP2D, may contribute to the Part B1 analysis.

Any patient who continues treatment with bemcentinib beyond confirmed disease progression will be followed for safety (AEs/SAEs) as well as general condition, performance status etc., as defined in protocol section 13.

16.4.2. Methods of Analysis

No formal statistical analysis will be performed. AEs will be coded using the Medical Dictionary for Regulatory Activities (MedDRA) Version 15.0 or above. The number and percentage of patients reporting treatment-emergent AEs will be tabulated by preferred term and system organ class and summarized by both CTCAE grade and relationship to study drug. All AEs commencing prior to dosing with study medication will be excluded from the tabulation but will be fully listed. AEs that have missing onset dates will be considered to be treatment-emergent, unless the stop date is known to be prior to the first administration of bemcentinib.

Separate listings will be produced for DLTs, SAEs, discontinuations due to related AEs, and events of ≥Grade 3 severity.

Summary statistics by dose cohort and time point will be produced for vital signs, ECG parameters and laboratory safety data, together with changes from baseline. The incidence of laboratory test results outside the normal range will be summarized by dose cohort and time point. Laboratory test results outside the normal range will be individually listed for clinical review. Abnormal ECG results will be summarized by dose cohort.

Changes in PR, QT interval and QTcF duration will be analyzed according to administered dose and ultimately modelled with corresponding plasma concentrations of bemcentinib when available.

Any patient treated with bemcentinib beyond disease progression will be followed for the same safety and efficacy assessments as for all other patients enrolled into the study. The data for patients treated beyond progression will be presented in both a combined output (with all patients) and also a separate output (reflecting a new period of analysis with the data collected in this period). All data collected will be included in the study CSR and may be presented at congress/symposia.

